2. Biomarker tests performed in the research lab (e.g. antibody titers, cytokine levels) at days 0, 1, 3, 7 and 14 (additional days 21 and 28 may be included, as available) in the recipient.

Study population:

Plasma Donor Inclusion Criteria for Enrollment

- Age greater or equal to 18
- Able to donate blood per blood bank standard guidelines
- Prior diagnosis of COVID-19 documented by a laboratory test. Patients outside of the UCMC medical system will be asked to provide documentation of COVID-19 positive test
- Complete resolution of symptoms at least 28 days prior to donation
- Female donors who have never been pregnant, previously pregnant female donors negative for HLA antibodies (HLA screening), or male donors

Plasma Donor Subject Exclusion Criteria for Enrollment

- Does not provide consent
- Does not meet standard blood bank donation guidelines
- Unsuccessful blood donation

Convalescent plasma donor subjects are consenting for plasma donation towards hospitalized patients with severe or life-threatening COVID-19 disease. Convalescent plasma units in the UCM Blood Bank collected under this protocol will be used for the currently approved Expanded Access Protocol IRB20-0825.

Plasma Recipient Subject Inclusion Criteria for Enrollment

[figure not shown]
- Patients must be 18 years of age or older
- Must have laboratory-confirmed COVID-19
- Must have severe or immediately life-threatening COVID-19
 - Severe defined as dyspnea, respiratory frequency \geq 30/min, blood oxygen saturation \leq 93%, partial pressure of arterial oxygen to fraction of inspired oxygen ratio $<$ 300, and/or lung infiltrates $>$ 50% within 24 to 48 hours
 - Life-threatening defined as respiratory failure, septic shock, and/or multiple organ dysfunction or failure. Lower priority should be given to patients with septic shock or multiple organ dysfunction or failure since their disease may have progressed to a point where they are not able to benefit from convalescent plasma therapy.

- Must be less than 21 days from the start of illness
- Patient is willing and able to provide written informed consent and comply with all protocol requirements. If the patient is not able to consent, we will obtain consent from the power of attorney or a health care proxy for the patient as determined by the Illinois Healthcare Surrogate Act
- Patient, power of attorney or health care proxy agrees to storage of specimens for future testing.

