The theoretical risk involves the phenomenon of antibody-mediated enhancement of infection (ADE). ADE can occur for several viral diseases and involves an enhancement of disease in the presence of certain antibodies. For coronaviruses, several mechanisms for ADE have been described and there is the theoretical concern that antibodies to one type of coronavirus could enhance infection to another viral strain (12). It may be possible to predict the risk of ADE of SARS-CoV-2 experimentally, as proposed for MERS. Since the proposed use of convalescent plasma in the COVID-19 pandemic would rely on preparations with high titers of neutralizing antibody against the same virus, SARS-CoV-2, ADE may be unlikely. The available evidence from the use of convalescent plasma in patients with SARS1 and MERS (13) and anecdotal evidence of its use in patients with COVID-19 (http://www.xinhuanet.com/english/2020-02/28/c_138828177.htm, <https://www.medrxiv.org/content/10.1101/2020.03.16.20036145v1.full.pdf>), suggest it is safe. However, because of these potential risks, we are limiting administration of SARS-CoV-2 convalescent plasma to patients with severe or life-threatening COVID-19 at this time. Caution and vigilance will be required for any evidence of enhanced infection.

Another theoretical risk is that antibody administration to those exposed to SARS-CoV-2 may avoid disease but modify the immune response such that those individuals mount

attenuated immune responses, which would leave them vulnerable to subsequent re-infection. In this regard, passive antibody administration before vaccination with respiratory syncytial virus was reported to attenuate humoral but not cellular immunity (14). If the concern proved real, these individuals could be vaccinated against COVID-19 when a vaccine becomes available. Furthermore, this issue will be investigated by measuring immune responses in those exposed and treated with convalescent plasma to prevent disease in an ongoing clinical trial. In addition, once serum antibody testing becomes readily available, immunity can be more reliably assessed. *These concerns seem modest compared to the possibility of limiting the duration and severity of disease, and avoiding interventions like mechanical ventilation, ARDS and sepsis.*

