Unanticipated Problem (UP)

Unanticipated problems involving risks to subjects or others refer to a problem, event or information item that is not expected, given the nature of the research procedures and the subject population being studied; and which suggests that the research places subjects or others at a greater risk of harm or discomfort related to the research than was previously known. The IRB considers unanticipated problems, in general, to include any incident, experience, or outcome that meets ALL of the following criteria:

1. unexpected (in terms of nature, severity, or frequency) given (a) the research procedures that are described in the protocol-related documents, such as the IRB-approved research protocol, investigator's brochure, drug or device product information, informed consent document, or other research materials; and (b) the characteristics of the subject population being studied, including underlying diseases, behaviors, or traits;
2. related or possibly related to participation in the research (possibly related means there is a reasonable possibility that the incident, experience, or outcome may have been caused by the procedures involved in the research); and

3. suggests that the research places subjects or others at a risk of unknown harm or addition/increased frequency of harms (including physical, psychological, economic, legal, or social harm) than was previously known or recognized.

Unanticipated problems may be adverse events, protocol deviations, noncompliance or other types of problems, but MUST meet all of the criteria listed above. It is the expectation of the IRB that all approved protocol procedures are being followed without alteration unless the IRB has been informed of a protocol change or deviation.

Protocol Deviation: Deviation from the IRB-approved study procedures. Designated serious and non-serious

1. **Serious Protocol Deviation:** Protocol deviation that is also an SAE and/or compromises the safety, welfare or rights of subjects or others
2. **Safety Reporting Requirements**

Reporting Interval

All AEs and SAEs will be documented from the first administration of study product until completion or un-enrollment from the study. All AEs and SAEs will be followed until resolution even if this extends beyond the study-reporting period. Resolution of an adverse event is defined as the return to pre-treatment status or stabilization of the condition with the expectation that it will remain chronic.

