- 4 = Life-threatening: Marked escalation of medical intervention/therapy required.
- 5= Death

Assessment of Association

The association assessment categories that will be used for this study are:

- Associated – The event is temporally related to the administration of the study product and no other etiology explains the event.
- Not Associated – The event is temporally independent of the study product and/or the event appears to be explained by another etiology.

The investigator must provide an assessment of association or relationship of AEs to the study product based on:

- Temporal relationship of the event to the administration of study product;
- Whether an alternative etiology has been identified;
- Biological plausibility;
- Existing therapy and/or concomitant medications.

Safety Oversight

Monitoring Plan

1. All AE and SAW will be reviewed by protocol team in real time.
2. An Independent Safety Monitor (ISM) has been appointed. The ISM is [name], who has expertise in infectious diseases and whose primary responsibility is to provide timely independent safety monitoring. An ISM is in close proximity to the study site and has the authority to readily access study participant records. The ISM reviews any SAE that occurs at the study site in real time and provides a written assessment.

Study monitoring

1. As per ICH-GCP 5.18 and FDA 21 CFR 312.50, clinical protocols are required to be adequately monitored by [name], the research team and the Office of Clinical research (OCR). Monitors will verify that
 - a. There is documentation of the informed consent process and signed informed consent documents for each subject
 - b. There is compliance with recording requirements for data points
 - c. All SAEs are reported as required
 - d. Individual subjects' study records and source documents align
 - e. Investigators are in compliance with the protocol.
 - f. Regulatory requirements as per Office for Human Research Protections-OHRP, FDA, and applicable guidelines (ICH-GCP) are being followed.

Halting Criteria for the Study

In the event that any of the 6 events listed under “Halting Criteria for the Study” occur, the IRB will be immediately notified and the study placed on hold until such time as the IRB agreed that study activities could resume.

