The study enrollment and dosing will be stopped and an ad hoc review will be performed if any of the specific following events occur or, if in the judgment of the study physician, subject safety is at risk of being compromised:

1. Death within one hour of plasma infusion
2. Occurrence of a life-threatening allergic/hypersensitivity reaction (anaphylaxis), manifested by bronchospasm with or without urticaria or angioedema requiring hemodynamic support with pressor medications or mechanical ventilation. , TRALI, TACO
3. One subject with an SAE associated with study product.
4. Two subjects with a Grade 3 or higher lab toxicity for the same parameter associated with study product.
5. An overall pattern of symptomatic, clinical, or laboratory events that the medical monitor, ISM, or SMC consider associated with study product and that may appear minor in terms of individual events but that collectively may represent a serious potential concern for safety.
6. Any other event(s) which is considered to be a serious adverse event in the good clinical judgment of the responsible physician. This will be appropriately documented.

Upon completion of this review and receipt of the advice of the ISM, the IRB will determine if study entry or study dosing should be interrupted or if study entry and study dosing may continue according to the protocol.

Halting Criteria/Rules for Subject Infusion

Infusion of study drug will be halted if any of the following manifestations of anaphylaxis develop and will not be restarted:

- Skin or mucous membrane manifestations: hives, pruritus, flushing, swollen lips, tongue or uvula
- Respiratory compromise: dyspnea, wheezing, stridor, hypoxemia
- A decrease in systolic blood pressure to < 90 mmHg or >30% decrease from baseline or a diastolic drop of >30% from baseline.

- Tachycardia with an increase in resting heart rate to > 130bpm; or bradycardia <40 that is associated with dizziness, nausea or feeling faint.
- Any other symptom or sign which in the good clinical judgment of the study clinician or supervising physician warrants halting the infusion. For example, the rapid onset of gastrointestinal symptoms, such as nausea, vomiting, diarrhea, and cramps, for instance, may be manifestations of anaphylaxis and may warrant an immediate halt prior to meeting full SAE criteria

Ethics/Protection of human subjects

Ethical Standard

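### The two-category causality scale has no level for possible or contributory causation, so COVID-like harms will tend to be classed Not Associated and then cannot meet halting items 3 and 4

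*Combined protocol and SAP*

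**What the plan says.** Assessment of Association sets a scale with exactly two levels. To be classed as Associated, an AE must pass a double test: "The event is temporally related to the administration of the study product and no other etiology explains the event". Both halves of that test have to be met. The other level, Not Associated, is reached more easily, because its conditions are joined by an and/or: "The event is temporally independent of the study product and/or the event appears to be explained by another etiology".

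Below the definitions comes a list of considerations ("The investigator must provide an assessment of association or relationship of AEs to the study product based on"): timing, alternative etiology, biological plausibility, and existing or concomitant therapy. Nothing says how these weigh against the two definitions. An on-site investigator makes the causality call (Investigator's Assessment of Adverse Events), and the relationship is recorded for every AE (Collection and reporting of SAEs and AEs).

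Four other parts of the protocol bear on this scale:

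- Recipient inclusion criteria: "Must have severe or immediately life-threatening COVID-19".
- Known potential risks, on antibody-mediated enhancement: "Caution and vigilance will be required for any evidence of enhanced infection".
- Halting Criteria for the Study, item 3: "One subject with an SAE associated with study product". Item 4 likewise requires association, for a repeated laboratory toxicity in two subjects.
- Unanticipated Problem (UP): "possibly related means there is a reasonable possibility that the incident, experience, or outcome may have been caused". In addition, the end of the reporting-interval text makes mere suspicion of a link enough for SAEs that come to light after study completion.

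**The concern.** The two definitions are not symmetric. Associated needs good timing and the absence of another explanation. For Not Associated, an apparent other explanation is sufficient, even when the timing fits plasma. An event to which both COVID-19 and plasma contributed has no category of its own.

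That matters more here than in most trials, because the competing explanation is present in every recipient by design. Respiratory worsening, shock or organ failure will usually have COVID-19 as a ready candidate cause. Antibody-mediated enhancement, as the protocol describes it, is a worsening of that same disease, so the scale is poorly suited to attributing a harm for which the protocol asks vigilance. There is no control arm, so no between-group comparison can recover a signal that case-by-case classification misses.

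At stake are the two halting items that require association, and any summary of how many events were related to plasma.

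**Working it through.** The documents give no operating characteristics for the halting rules and no expected SAE rates, so there is no planned figure to reproduce. The check is mainly of the text, followed by an illustration on assumed inputs.

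**1. Relatedness standards side by side**

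| Where | Test | Temporally related event, with both COVID-19 and plasma plausible |
|---|---|---|
| Assessment of Association | No other explanation | Not Associated, if COVID-19 appears to explain it |
| Unanticipated Problem (UP) | Reasonable possibility | Possibly related |
| SAE learned of after study completion | Suspicion of a link | Reportable |

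The same event can therefore be possibly related in one section and Not Associated in another.

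**2. Which halting routes use association**

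| Route | Needs association? |
|---|---|
| Item 1 (death in the first hour) | No |
| Item 2 (anaphylaxis, TRALI, TACO) | No |
| Item 3 (one SAE) | Yes |
| Item 4 (same laboratory toxicity in two subjects) | Yes |
| Item 5 (overall pattern) | Uses the word, but rests on what the medical monitor, ISM or SMC think of the pattern; not expressly tied to the investigator's category |
| Item 6 (any other SAE in the physician's judgment) | No |
| Lead-in safety trigger (study physician's judgment) | No |

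Only items 3 and 4 are closed to an event once it is classed Not Associated. Separately, the independent safety monitor reviews every SAE and writes an assessment, whatever its category.

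**3. Which analyses use association**

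Analysis of AE data plans the proportions with an SAE and with a Grade 3 or higher AE. The primary safety endpoints are rapid deterioration and the cumulative incidence of SAEs. None is filtered by causality. Only a summary of the recorded relationships would be affected.

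**4. Illustration for items 3 and 4**

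Inputs: n = 10 recipients (Protocol Summary). Assumed: p, the risk per recipient of a qualifying event truly caused by plasma; and s, the share of those events classed Associated.

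Item 3 needs at least one Associated SAE: P = 1 − (1 − p·s)^10.

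- p = 0.10, s = 1: 1 − 0.90^10 = 65.1%
- p = 0.10, s = 0.5: 1 − 0.95^10 = 40.1%
- p = 0.10, s = 0.2: 1 − 0.98^10 = 18.3%

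| p | s = 1 | s = 0.5 | s = 0.2 | s = 0.1 |
|---|---|---|---|---|
| 0.10 | 65.1% | 40.1% | 18.3% | 9.6% |
| 0.20 | 89.3% | 65.1% | 33.5% | 18.3% |
| 0.30 | 97.2% | 80.3% | 46.1% | 26.3% |

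Item 4 needs two subjects: P = 1 − (1 − q)^10 − 10q(1 − q)^9, with q = p·s and p now the risk of the laboratory toxicity. At p = 0.10 this is 26.4% for s = 1, 8.6% for s = 0.5 and 0.4% for s = 0.1.

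**5. Item 6 for comparison**

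Read literally, item 6 fires on any other SAE. With an assumed any-cause SAE risk b, P = 1 − (1 − b)^10, which is 89.3%, 97.2% and 99.9% for b = 0.20, 0.30 and 0.50. On that reading, the association condition in item 3 does almost nothing. If item 6 is meant more narrowly, association again becomes the main filter for SAEs outside items 1 and 2. The text does not say which is intended.

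**The case against.** A reader might infer that no COVID-like harm can ever be Associated. The text does not go that far. The test is whether another etiology explains the event, not whether one exists, and the investigator must also weigh timing and biological plausibility. An abrupt deterioration during infusion need not be put down to COVID-19. This stands, and it is why the point is about a tendency.

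A reader might also infer that enhancement could not halt the study. It could: through item 5 or 6, the physician's safety judgment, or action following the monitor's review. This stands too, with a limit. Items 1 and 2 describe specific acute events and not enhancement developing over days, and the remaining routes rest on judgment or, for item 6, on wording whose reach is unclear.

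Nor do the documents support a claim that the safety results as a whole are biased, since the planned proportions and endpoints count events regardless of cause. The protocol also does not present enhancement as the leading risk; it calls the risk theoretical and considers it possibly unlikely.

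The two relatedness standards can be defended as serving different purposes. The unanticipated-problem definition has three joint criteria and concerns participation in the research, while the association scale concerns the product. So they are not a formal contradiction. The practical mismatch remains: one event can receive opposite labels, and only the stricter label feeds items 3 and 4.

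Finally, in 10 uncontrolled recipients no wording will separate enhancement from progression in a single case. That is true, but it favors a scale that can record uncertainty.

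**Conclusion.** The concern holds in limited form. The scale has no place for possible or contributory causation, and in this population it will tend to push COVID-like harms into Not Associated. Once there, they cannot meet halting items 3 and 4, and the recorded relationships lean toward unrelated. The effect is confined to those two items and to any relatedness summary.

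The size cannot be derived from the documents. The fall from 65% to 40% to 18% rests on an assumed 10% plasma-caused SAE risk and assumed attribution shares, treats recipients as independent, and describes item 3 alone. It should not be read as a fall in the overall chance of stopping.

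A separate inconsistency needs settling in any case: item 6 read literally makes the association condition in item 3 nearly redundant.

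**What to change.** 1. Align the causality categories with the reasonable-possibility standard already in the unanticipated-problem definition, or add a possibly associated level. State how the listed factors, such as biological plausibility, bear on the category.
2. Tabulate the independent safety monitor's written assessment beside the investigator's category for each SAE. The assessment already exists under Safety Oversight; only the table is new. Keep the planned SAE and Grade 3 or higher AE proportions unfiltered by causality.
3. Have the sponsor and IRB reconcile Unanticipated Problem (UP), Assessment of Association and Halting Criteria for the Study, and state how items 3 to 6 use association. How those items should then operate is theirs to decide.

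Cost: wording and one table. The downside is real: more events will be classed as associated and, because item 3 needs only one subject, some extra ad hoc reviews will follow. That is why step 3 belongs with step 1. Overall this is a cheap improvement.

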- If an AE develops during infusion, the infusion may be slowed or stopped as per investigator's decision.
 - Most reactions to plasma are relatively minor and the infusion can generally be continued. Infusion site burning and non-allergic systemic effects can generally be managed with slowing of the infusion. Infusion can generally be continued in cases of itching or hives after pausing the transfusion, administering antihistamines, and observing the patient for worsening.
 - Severe allergic reactions such as, bronchospasm and hypotension, and may require discontinuation of the infusion.

Concomitant medications will be documented on the CRF

- Prescription medications
- Over the counter medications

- Herbal treatments/nutritional supplements
- Blood products

Statistical considerations

Statistical Analysis

This is a pilot study focused on determining the protocol feasibility with limited subject enrollment. Therefore, statistical analysis will include descriptive summaries of both the primary and secondary outcomes of interest. For continuous variables we will determine: median, minimum and maximum values. Categorical variables will be summarized by the frequency. Unless otherwise indicated, percentages in tables will be column percentages, using the total number of observations in the population ($n=10$), as the denominator. Percentages will be rounded to one decimal place, and thus may not always add up to exactly 100%. Clinical laboratory values will be first reported in using International System of Units (SI).

Analysis of AE data

Analysis of AE data will primarily be descriptive based on MedDRA coding of events. The proportion of subjects experiencing an SAE and the proportion experiencing a Grade 3 or higher AE will be measured.

Analysis of SARS-CoV-2 viremia

Analysis of SARS-CoV-2 viremia will primarily be descriptive, comparing the viremia levels at days 0,1,3,7 and 14 between the subject recipients.

Analysis of research biomarkers

Analysis of biomarker tests performed in the research lab such as antibody titers, cytokine levels will primarily be descriptive, comparing the titers at days 0,1,3,7 and 14 between subject recipients.

Endpoints

Primary Endpoint:

1. Feasibility of performing study pathway consisting of consenting convalescent donors, harvesting convalescent plasma, application for FDA eIND and administering convalescent plasma to the patients

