At any time after completion of the study, if the investigator becomes aware of a SAE that is suspected to be related to study product, this will be reported.

Collection and reporting of SAEs and AEs. Documentation of adverse events will be determined by the clinician and recorded on the Clinical Adverse Event Report form and will include the following information: Description of the condition, dates of condition, treatment of condition (medications, doses, dates), whether emergency treatment was required, treatment outcome, relationship of the adverse event to the study medication(s) and severity of the event. Additional information about the AE will be provided as needed so as to understand the scope of the event.

Management of SAEs. Serious adverse events are always managed, first and foremost, based on medical appropriateness so as to ensure subject safety. The PIs are notified as soon as possible about an SAE and will work with the medical team to ensure the best resolution possible of the problem. In medical emergencies the PIs are permitted to provide all health-care providers with appropriate medical information at hand about the subject consistent with HIPAA regulations.

Serious adverse events will be forwarded by the PI to the Independent Safety Monitor and IRB immediately. Fatal or life-threatening unexpected SAEs will be reported to the

IRB immediately. Non-fatal, non-life-threatening unexpected SAEs will be reported to the Independent Safety Monitor within 72 hours.

Investigator's Assessment of Adverse Events

The determination of seriousness, severity, and causality will be made by an on-site investigator who is qualified (licensed) to diagnose adverse event information, provide a medical evaluation of adverse events, and classify adverse events based upon medical judgment. This includes but is not limited to physicians, physician assistants, and nurse practitioners.

Laboratory abnormalities will be reported as AEs if there is a 2 s.d. increase above baseline.

Assessment of Seriousness

1. Event seriousness will be determined according to the protocol definition of an SAE
2. Assessment of Severity

Event severity will be assigned according to the scale below

- 1 = Mild: Transient or mild discomfort (<48 hours); no medical intervention/therapy required.)
- 2 = Moderate: Some worsening of symptoms but no or minimal medical intervention/therapy required)
- 3 = Severe: Escalation of medical intervention/therapy required

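### Halting item 4 depends on a laboratory grade that the protocol's only severity scale does not define by laboratory value

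*Combined protocol and SAP*

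**What the plan says.** Under Halting Criteria for the Study, item 4 stops enrollment and dosing, pending review, on this event: "Two subjects with a Grade 3 or higher lab toxicity for the same parameter associated with study product".

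The protocol has one severity instrument for adverse events, under Investigator's Assessment of Adverse Events. It is introduced without any exception for laboratory events: "Event severity will be assigned according to the scale below". Its levels are:

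- The lowest level is given as "1 = Mild: Transient or mild discomfort (<48 hours); no medical intervention/therapy required".
- One step up, just below item 4's threshold, stands "2 = Moderate: Some worsening of symptoms but no or minimal medical intervention/therapy required".
- The level at which item 4 starts to count is worded "3 = Severe: Escalation of medical intervention/therapy required".
- The level after that one is "4 = Life-threatening: Marked escalation of medical intervention/therapy required".
- Level 5 is death.

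Just before the scale stands the only numeric laboratory criterion for adverse events: "Laboratory abnormalities will be reported as AEs if there is a 2 s.d. increase above baseline".

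The grades are used again under Analysis of AE data, where "the proportion experiencing a Grade 3 or higher AE will be measured". The Statistical Analysis section sets the denominator for percentages at 10.

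**The concern.** Item 4 is the only halting item with a countable laboratory threshold, so its grade has to mean the same thing whoever assigns it. The scale that supplies the grade was written for clinical events. It describes discomfort, symptoms and the treatment needed. It does not describe how far a value has moved.

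If the scale is followed as written, the same marked abnormality could appear in two recipients and not count, because neither needed more than minimal intervention. The grade would then reflect clinical management rather than the toxicity that item 4 names. The same weakness reaches the Grade 3 or higher proportion wherever a laboratory event is the one that decides a recipient's status.

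**Working it through.** The plan states no operating characteristic for item 4, so there is no figure to reproduce. The check is a reading of the text, followed by one illustration under stated assumptions.

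**Step 1. Where could a laboratory grade come from?**

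| Place in the protocol | What it does | Gives a laboratory grade? |
|---|---|---|
| Severity scale, levels 1 to 5 | Grades by discomfort, duration, symptoms and intervention required | No level mentions a value, a multiple of normal or a change from baseline |
| 2 s.d. rule | Decides whether a laboratory change is an adverse event; names increases only | No |
| MedDRA, Analysis of AE data | Codes events | No |
| 7-point ordinal scale | Clinical status | No |

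No laboratory toxicity table or external grading standard is named.

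**Step 2. Apply the scale to a laboratory value.** Between levels 2 and 3, the intervention wording moves from none or minimal to escalation. Nothing else in the level 3 description marks the boundary apart from the label Severe.

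- Marked abnormality, some symptoms, no or minimal intervention required: level 2.
- Marked abnormality, short-lived, no intervention required: nearest to level 1, although level 1 speaks of discomfort.
- Marked abnormality, no symptoms, lasting beyond 48 hours, no intervention required: level 1 is limited to under 48 hours, level 2 asks for worsening symptoms, and levels 3 and 4 ask for escalation. No level fits.
- Abnormality of any size for which escalation is required: level 3 or 4.

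The size of the abnormality enters only through the investigator's view of what it requires.

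**Step 3. Carry this to item 4.** The rule needs two recipients. If exactly two have a qualifying toxicity in the same parameter, grading one of them below 3 is enough for item 4 not to be met (2 − 1 = 1, below the required 2).

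**Step 4. Illustration, with rates that are assumptions and not in the documents.** Let p be the chance that a recipient has a product-associated marked abnormality in one given parameter, and s the share of these graded 3 or higher under the scale. Take recipients as independent and all 10 as treated. With q = p × s,

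P(item 4 met) = 1 − (1 − q)^10 − 10q(1 − q)^9.

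For p = 0.20 and s = 1, q = 0.20: 1 − 0.107 − 0.268 = 0.624 (from unrounded terms).

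| p | s = 1 | s = 0.5 | s = 0.25 |
|---|---|---|---|
| 0.10 | 0.264 | 0.086 | 0.025 |
| 0.20 | 0.624 | 0.264 | 0.086 |
| 0.30 | 0.851 | 0.456 | 0.170 |

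The table shows how strongly the rule depends on s, a quantity that the protocol leaves open. It does not estimate what will happen in this trial, and it ignores the other halting items.

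**Step 5. The Grade 3 or higher proportion.** With a denominator of 10, one recipient is 1/10 = 10 percentage points. A regraded laboratory event moves the proportion only if that recipient has no other adverse event of Grade 3 or higher. Otherwise the shift is zero.

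**The case against.** The strongest case on the other side has four parts.

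**Judgment.** The scale asks what intervention is required, not what was given, and a licensed investigator assigns severity by medical judgment. A dangerous value left untreated can therefore be graded 3 or 4, and a modest correction can count as minimal and be graded 2. This stands. A reader might infer that any large untreated value is Grade 1 or 2 and any modest treated value is Grade 3. The text does not support that: treatment given is not the test, and some untreated values fit no level at all. But leaving the grade to judgment also leaves item 4 without a fixed threshold.

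**Association.** A reader might also infer that item 4 will fire on routine corrections. Under Assessment of Association, an event counts as associated only if it is temporally related to the product and no other cause explains it. Item 4 also needs two subjects and the same parameter. In recipients with severe or life-threatening COVID-19, other causes will be common. False triggers are therefore limited. The filter does nothing for a toxicity that has been graded too low. Falls in a value, such as in hemoglobin, make weak examples because the 2 s.d. rule names only increases.

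**Backstops.** Item 5 covers patterns of laboratory events that look minor one by one, item 3 covers an associated serious event, and item 6 covers other events judged serious. The study physician may also stop the study on judgment, and events are reviewed in real time. These soften the risk of a missed signal, item 5 most directly. However, items 3 and 6 need a serious event, which a laboratory change under observation need not be, and item 5 is discretionary. None defines a laboratory grade.

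**Size of the effect on the analysis.** It is tempting to say that every misgrade shifts the Grade 3 or higher proportion by 10 points, or that the result cannot be compared with other plasma series. Neither is supported. The proportion counts all adverse events whatever their cause, so many recipients may qualify on other grounds, and this descriptive pilot plans no such comparison.

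**Conclusion.** The concern holds in a limited form. Item 4 refers to a laboratory grade, and the scale that the protocol prescribes has no laboratory content and separates Grade 2 from Grade 3 by required intervention alone. A marked abnormality needing little or no intervention can fall outside item 4, and two graders can differ on one value while both follow the protocol. The risk lies mainly in missed signals.

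Item 4's loss of sensitivity cannot be calculated from the documents. Under the assumed rates above, halving the share graded 3 or higher lowers the chance of meeting item 4 from 0.624 to 0.264 at p = 0.20. The effect on the Grade 3 or higher proportion is between 0 and 10 percentage points for each recipient affected.

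The conclusion rests on the protocol text being complete on grading. Safety is a named primary objective and the halting rules operate at this sample size, so the gap should be closed, although the backstops keep it from leaving the study without laboratory safety oversight.

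**What to change.** Reconcile the severity scale with halting item 4:

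- Keep the existing scale for clinical events.
- State that laboratory abnormalities are graded by value from one published laboratory toxicity table, chosen and named by the sponsor.
- Record the Day 0 grade for each parameter, so that later grades can be interpreted against it.
- Use these grades wherever the protocol refers to laboratory toxicity of Grade 3 or higher, and for laboratory events in the Grade 3 or higher proportion.

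The cut-offs, the handling of abnormalities already present at baseline in item 4, and the item's count and hold are for the sponsor and the safety monitor to settle.

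The cost is a sentence, a reference to the table and a little grading work. The safety laboratory tests are already scheduled for days 0 to 7 and day 14 under Monitoring procedures, so no new data are needed. The Grade 3 or higher proportion may change in either direction.
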